9.1.5 Spirometry

Volunteers will perform spirometry at the screening visit and throughout the study period.

9.1.6 Bronchodilator Reversibility or Methacholine Challenge or Exercise Testing

For volunteers with asthma, as part of their screening they will be asked to perform either bronchodilator reversibility, methacholine challenge or challenge testing as per latest CUH policy (e.g. exercise testing), to confirm bronchial hyperreactivity. If their baseline FEV₁ is $\leq 80\%$, they will be asked to perform spirometry before and after inhalation of salbutamol to check for reversibility by $\geq 12\%$ and 200 mL. If their baseline FEV₁ is $\geq 80\%$ they will instead perform a methacholine challenge or challenge test as per CUH policy (e.g. exercise test).

9.2 Informed Consent

A written or electronic version of the Participant Information Sheet (PIS) will be provided to participants detailing the nature of the study and any known side effects and risks involved in taking part. The participant will be free to withdraw from the study at any time for any reason without prejudice to future care, and with no obligation to give the reason for withdrawal.

The participant will be allowed time to consider the information, and the opportunity to question the Investigator, to decide on participation in the study. Electronic Informed Consent (eConsent) will then be obtained by means of participant dated and investigator dated electronic signatures. The person obtaining consent will be suitably qualified and experienced and have been authorised to do so by the PI as detailed on the Delegation log for the study. A copy of the signed form will be retained in the Trial Master File (TMF). A written or electronic copy of the signed consent form will also be provided to participants.

9.3 Screening and Eligibility Assessment

Participants in this study will be recruited from Cambridge University Hospitals (CUH), Royal Papworth Hospital (RPH), Heart and Lung Research Institute (HLRI), University of Cambridge, volunteer databases, local advertising in the Cambridge area and wider East of England region, as well through online platforms. Participants from CUH may be recruited from outpatients (in particular, departments of allergy and asthma) or comprise of staff working there. Employees or students at the University of Cambridge who express an interest in taking part are also eligible. Advertisements for the study will be through organisational posters, newsletters, online bulletins, local newspapers, online platforms, and social media channels.

Pre-screening of interested participants will primarily involve interaction with a dedicated study website (www.lungchallenge.org.uk) or by email and telephone screening. They will be able to download the Participant Information Sheet (PIS) from the study website.

An online pre-screening questionnaire hosted using REDCap software will be utilised to ascertain basic eligibility for the study in an anonymised form. If participants are not eligible no data will be stored. If participants may be eligible, they will be asked for further demographic and medical details to help ascertain eligibility and their data will be stored using the University of Cambridge's Secure Data Hosting Service which has a Safe Haven for Personal Identifiable Data <https://cscs.medschl.cam.ac.uk/server-services/secure-data-hosting-service/>.

Subsequently, for potentially eligible participants, a screening visit will be undertaken at the Cambridge Clinical Research Centre (CCRC) to evaluate the following:

Demographics: date of birth, gender, race, smoking status.

Medical History: Details of any history of disease or surgical interventions and systems review to determine inclusion/exclusion criteria.

Concomitant Medication: All over the counter or prescription medication, vitamins, and/or herbal supplements will be recorded.

Physical Examination as well as physiological observations, height, weight, and temperature will be recorded.

ECG Test: A 12-lead ECG will be undertaken for each participant.

Laboratory Tests: Biochemistry, full blood count, liver function test, total IgE, PBMC isolation, skin prick allergy testing, and a pregnancy test (for women) will be performed.

Nasal Brushing: At the discretion of the Investigator, this will be done to collect nasal epithelial cells.

Induced Sputum: Volunteers will undergo induced sputum sampling. For volunteers with asthma this will take place at a second screening visit approximately 7 days (+/- 3 days) after

the reversibility testing is done at the screening visit. This is to limit any confounding effects of reversibility testing on cellular counts in the induced sputum.

All screening results will be reviewed by the Investigator to determine participant eligibility.

For participants in the “sample only” part of the study, their screening will briefly involve collection of data on demographics, medical history, medication usage, spirometry, and physiological observations to ensure they meet the inclusion and exclusion criteria. They will not require other screening tests. Sample collection will involve a nasal brushing, induced sputum, and blood sampling (20 mL – for isolation of peripheral blood mononuclear cells). This will be the end of the study for them.

9.4 Subsequent Assessments

For volunteers who are eligible for the study, the following study visits and procedures will take place and are outlined in [Appendix B](#).

9.4.1 Visit 1 (Day 1)

This will take place over 24 hours including an overnight stay in the CCRC. Baseline assessments will include:

- Spirometry
- Physiological observations (temperature, pulse, and blood pressure)
- Nasosorption - to determine baseline nasal immune profile
- Blood tests (FBC, CRP, Serum)

Volunteers will have been randomised to receive either R848 or saline via a breath-actuated nebuliser ([Aeroeclipse II](#)). After administration, they will be monitored at regular intervals by the clinical research team to check for clinical tolerability and repeat blood tests. The following morning after 24 hours, volunteers will subsequently have repeat blood tests as well as a repeat induced sputum performed.

9.4.2 Visit 2 (Day 2)

This will take place at 48 hours to monitor physiological observations, spirometry and perform blood tests.

9.4.3 Visit 3 (Day 8)

This will take place at 7 days after challenge to monitor physiological observations, spirometry and perform blood tests. This will then be the end of the study for participating volunteers.

9.5 Definition of End of Trial

The end of trial is the date of the last visit of the last participant.

9.6 Discontinuation/Withdrawal of Participants from Study Treatment

Each participant has the right to withdraw from the study at any time. In addition, the investigator may discontinue a participant from the study at any time if the investigator considers it necessary for any reason including:

- Ineligibility (either arising during the study or retrospective having been overlooked at screening)

- Significant protocol deviation
- Significant non-compliance with treatment regimen or study requirements
- An adverse event which requires discontinuation of the study or results in inability to continue to comply with study procedures
- Consent withdrawn

The reason for withdrawal will be recorded in the CRF. If the participant is withdrawn due to an adverse event, the investigator will arrange for follow-up visits or telephone calls until the adverse event has resolved or stabilised.

9.7 Source Data

Source documents are original documents, data, and records from which participants' CRF data are obtained. These include, but are not limited to, hospital records (from which medical and medicine history may be summarised), clinical and office charts, laboratory and pharmacy records, diaries, microfiches, radiographs, and correspondence.

CRF entries will be considered source data if the CRF is the site of the original recording (e.g., there is no other written or electronic record of data). All documents will be stored safely in confidential conditions. On all study-specific documents, other than the signed consent, the participant will be referred to by the study participant number and not by name.

10. TREATMENT OF TRIAL PARTICIPANTS

10.1 Description of Study Treatment

Challenge Agent	Manufacturer	Catalogue Dose	Production Purity
Resiquimod (R848) VacciGrade TLR7/8 agonist Synthetic vaccine grade	Invivogen, California [name] www.invivogen.com	5 mg lyophilized R848 Reconstitute in endotoxin-free physiological water CAS 144875-48-9	Non-biological origin: does not contain any animal nor human components. Endotoxin <1.25 EU/mg

R848 has been administered *in-vivo* in pre-clinical models and humans in a wide variety of formulations and routes at significantly higher doses than the proposed study, with extensive available data on tolerability:

- R848 was well tolerated in pre-clinical models in mice and rats (17, 18).
- Oral R848 has been given to patients with chronic hepatitis C infection and was well-tolerated at doses of 0.01mg/kg, equating to 700 µg for a 70 kg human (6).
- Topical dermal R848 is safe and effective as a skin cream for the treatment of anogenital warts, actinic keratosis and skin cancer. Human studies have been carried out giving topical R848 to inflamed skin with actinic keratoses at doses up to 0.25%, which is equivalent to 2500 µg/mL (19). A related compound, the TLR7 agonist Imiquimod (marketed as Aldara), is approved for clinical use as a topical application for genital warts.
- Nasal R848 at doses between 10-100 µg/mL has been given by the PI to 54 participants ranging from those who are healthy to those with allergic rhinitis and asthma. This was effective at inducing mucosal innate immune responses whilst being clinical tolerable (11, 12).

For the present study, R848 will be reconstituted as per the manufacturer's instructions and diluted to the appropriate doses at CUH. A sample of the prepared dose vials will be sent for external quality control sterility testing to British Pharmacopeia standards before use in the clinical study.

Saline will be obtained from commercial medicine stock from within the hospital. It will be manufactured to GMP and considered sterile therefore no additional sterility testing will be required.

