10.3 Storage of Study Equipment or Related apparatus

R848 will be stored in labelled storage vials in a -20°C freezer within CUH in PI's laboratory and defrosted on the day of usage. Saline will be stored at room temperature. All other clinical equipment will be stored either in the PI's laboratory or the CRF.

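### Prepared R848 vials are tested for sterility but not endotoxin, so a contaminant added in local dilution or vialling could not be told apart from an R848 effect on CXCL10

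*Combined protocol and SAP*

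**What the plan says.** On the active arm, section 10.1 states that "R848 will be reconstituted as per the manufacturer's instructions and diluted to the appropriate doses at CUH". The product table in the same section gives "Endotoxin <1.25 EU/mg" for the supplied material and the instruction "Reconstitute in endotoxin-free physiological water". It does not name the fluid for the later dilution steps. On release testing, section 10.1 says "A sample of the prepared dose vials will be sent for external quality control sterility testing to British Pharmacopeia standards before use". No other test on the prepared vials is described. Section 10.3 places storage, in labelled vials at -20°C, in the PI's laboratory.

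On the control arm, section 10.1 says "Saline will be obtained from commercial medicine stock from within the hospital", and then "It will be manufactured to GMP and considered sterile therefore no additional sterility testing will be required". Section 10.3 sets the two arms side by side: R848 is "defrosted on the day of usage. Saline will be stored at room temperature".

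The two arms are compared on CXCL10 at 24 hours (sections 7.2 and 12.1), with 4 participants on R848 and 2 on saline per cohort, by unpaired t-tests at P < 0.05 (section 12.3). Section 10.2 uses the same comparison for escalation: the next cohort opens if the difference is not significant and the dose is tolerable.

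**The concern.** The R848-saline contrast is meant to isolate R848. As planned, the arms also differ in reconstitution, dilution, vialling and freeze-thaw. The product is chosen to activate innate immunity and the readout is an innate-immune marker, so an innate-active impurity is the kind that matters most here. Randomisation and participant blinding do not help, because the difference lies in what is put into the nebuliser.

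A sterility test looks for viable organisms. A vial can pass it and still contain endotoxin. If a contaminant did raise CXCL10, the trial would credit the rise to R848. Under section 10.2 a significant difference means that the condition for opening the next cohort is not met, so the selected dose could rest on an effect that R848 did not cause. Section 5.2 intends the model for later use, so the error would carry forward. Unmeasured endotoxin in an inhaled product is also a safety matter.

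**Working it through.** The plan gives no figure on this point to reproduce. The check has three parts.

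**1. What each safeguard covers**

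| Step | R848 | Saline | Stated endotoxin control |
|---|---|---|---|
| Starting material | supplied powder | commercial GMP stock | powder limit 1.25 EU/mg |
| Reconstitution | yes | no | endotoxin-free water |
| Dilution to dose at CUH | yes | no | none stated; fluid not named |
| Storage vials, -20°C, thaw | yes | no | none stated |
| Test on prepared vials | sterility, on a sample | none beyond GMP | none stated |

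Both endotoxin controls sit above the dilution row.

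**2. What the powder limit bounds**

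Inputs: 1.25 EU/mg (section 10.1); concentrations c of 0.1, 1, 10 and 100 µg/mL and a volume of about 1 mL (section 10.2, which leaves the volume to be confirmed).

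Maximum endotoxin from powder = 1.25 EU/mg × (c ÷ 1000) mg/mL × 1 mL:

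- 0.1 µg/mL: 1.25 × 0.0001 = 0.000125 EU
- 1 µg/mL: 1.25 × 0.001 = 0.00125 EU
- 10 µg/mL: 1.25 × 0.01 = 0.0125 EU
- 100 µg/mL: 1.25 × 0.1 = 0.125 EU

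The powder's contribution is therefore bounded. What dilution and vialling add is not bounded by any stated test.

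**3. What a handling effect would do to the planned test**

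The documents give neither a contaminant level nor a CXCL10 standard deviation, so the shift d (in SD units, R848 arm only) is an assumption. R848 itself is given no effect. Further assumptions: normal data, equal variances and a two-sided test, since section 12.3 does not state sidedness.

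Degrees of freedom = 4 + 2 − 2 = 4. Noncentrality = d ÷ √(1/4 + 1/2) = d ÷ 0.866. The chance p of significance comes from the noncentral t distribution. For four healthy cohorts, taken as independent, with one sample type and the same shift in each, the chance of at least one false response is 1 − (1 − p)⁴, computed from unrounded p.

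| Shift d | p, one comparison | At least one in four cohorts |
|---|---|---|
| 0 | 5.0% | 18.5% |
| 0.5 SD | 7.4% | 26.4% |
| 1 SD | 14.7% | 47.0% |
| 2 SD | 42.2% | 88.9% |
| 3 SD | 73.7% | 99.5% |

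The 18.5% at d = 0 comes from repeated testing, not from contamination. The part due to handling is the excess over the first row: at 1 SD, 14.7 − 5.0 = 9.7 points per comparison and 47.0 − 18.5 = 28.5 points over four cohorts. At 4 SD, p is 92.4%, so a false result with 80% probability in one comparison needs a shift of between 3 and 4 SD.

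**The case against.** The strongest reply is that the risk is hypothetical. The powder has a tight limit, the reconstitution water is endotoxin-free, and the later diluent, if it is the same hospital saline, would be common to both arms. Nothing in the documents suggests contamination, the shifts above are assumed, and with 4 versus 2 only a large shift would reliably produce a false signal. All of this stands. It limits how much can be claimed, but it does not supply a measurement on the finished vials.

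A reader might infer several stronger points that the documents do not support:

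- **That a contaminant would be constant across doses and so show in the lowest cohort.** The dilution scheme is not given. If doses come from a common stock, a contaminant entering at reconstitution would be diluted with R848, by up to 100 ÷ 0.1 = 1000-fold, and would be smallest at the lowest dose. Only entry at final dilution or vialling would be roughly constant.
- **That endotoxin is known to raise CXCL10 here.** Section 7.1 cites inhaled LPS for the nebulisation technique. No section gives its effect on serum or sputum CXCL10 at 24 hours.
- **That the doses are made up in the PI's laboratory.** Section 10.1 places preparation at CUH; section 10.3 places only storage in that laboratory.
- **That the saline should have extra sterility testing.** The sentence on GMP saline is not in error.
- **That every cohort would be affected.** One contaminated batch need not reach all cohorts.
- **That freeze-thaw itself alters CXCL10.** The documents give no mechanism.

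**Conclusion.** The point holds as a conditional gap in the plan. Endotoxin or another innate-active impurity added during local dilution or vialling would fall in the R848 arm only, no stated test would detect it as long as the vial is sterile, and the planned contrast could not separate it from an R848 effect. That contrast is both the primary comparison and part of the escalation rule.

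The size cannot be fixed from the documents. Whether a contaminant is present, how much it would move CXCL10 and whether it would scale with dose are all unknown; the last depends on where it enters. Under the stated assumptions the false-positive chance per comparison runs from 5.0% with no shift to 42.2% at 2 SD. The recommendation rests less on these figures than on the absence of a finished-vial measurement that would be cheap to obtain.

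**What to change.** In section 10.1, amend the vial-testing sentence. Suggested wording: *Vials sampled from each prepared R848 batch will be tested externally for both sterility and bacterial endotoxin. No vial from the batch will be used until both results meet the limits stated in this section.* The endotoxin limit must be written in before the first batch is made; the documents give none for finished vials, and it is for the sponsor to set. Section 10.1 should also name the fluid used for the dilution steps after reconstitution.

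The cost is one added test per batch, on vials already being sent out. No dose, control or clinical rule changes. An endotoxin test caps one contaminant; it does not detect other innate-active impurities.

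An optional alternative is to make control vials from the same diluent lot and to vial, freeze and thaw them with the R848 vials. A contaminant from that shared handling would then shift both arms, and its expected contrast would be zero. The trade-off is that a GMP product is replaced by a locally prepared one, which extends the handling risk to control participants and needs its own sterility and endotoxin testing. The finished-vial endotoxin test does not depend on that choice.

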10.2 Dose Escalation

The following doses of nebulised R848 will be tested using a single dose escalation design: 0.1, 1, 10, 100 µg/mL. Six volunteers will be involved in each dose cohort with only a single dose given to each participant.

Each participant will be administered a dose of R848 or saline in a volume of approximately 1 mL (optimal volume to be confirmed after testing) using a breath-actuated nebuliser.

At the end of each dose cohort, CXCL10 levels in sputum and blood will be assessed and compared between saline and R848. If there are no statistically significant differences

between groups, and the dose is tolerable for volunteers, then the study will proceed to the next dose cohort.

Spirometry will be monitored regularly after inhaled challenge. Bronchodilator drugs will be available on standby for administration if volunteers have symptoms of breathlessness or tight chest associated with a significant drop in FEV₁ ($\geq 20\%$) from baseline.

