11. SAFETY REPORTING DEFINITIONS

11.1 *Adverse Event (AE)*

An AE or adverse experience is any untoward medical occurrence in a participant, which does not necessarily have a causal relationship with the intervention. An AE can therefore be any unfavourable and unintended sign (including an abnormal laboratory finding), symptom or disease temporally associated with the study, whether or not considered related to the study.

11.2 *Serious Adverse Event (SAE)*

A serious adverse event or reaction is any untoward medical occurrence that at any dose:

- Results in death,
- Is life-threatening,

NOTE: The term "life-threatening" in the definition of "serious" refers to an event in which the participant was at risk of death at the time of the event; it does not refer to an event which hypothetically might have caused death if it were more severe, including an event which:

- Requires inpatient hospitalisation or prolongation of existing hospitalisation,
- Results in persistent or significant disability/incapacity, or
- Is a congenital anomaly/birth defect.
- Other important medical events*

*Other events that may not result in death, are not life threatening, or do not require hospitalisation, may be considered a serious adverse event when, based upon appropriate medical judgement, the event may jeopardise the patient and may require medical or surgical intervention to prevent one of the outcomes listed above.

Planned admission to hospital for a pre-existing condition will not be considered an SAE.

11.3 *Expected Adverse Events and Serious Adverse Events Exempt from Recording*

Nasal R848 challenge administered at doses between 10 - 100 µg/mL in healthy participants and those with asthma has previously been well tolerated with no reported SAEs (11, 12).

R848 is a synthetic substance that when given to in the respiratory tract is designed to mimic the effects of a viral infection such as influenza. Therefore, expected AEs that participants may experience include transient flu-like symptoms such as:

- Cough
- Runny nose
- Mild headache
- Low grade fever
- Lethargy
- Myalgia

If a high-grade fever occurs that is more sustained or causes symptoms, then volunteers will be offered an antipyretic such as paracetamol.

Participants with asthma will be carefully monitored after R848 dosing. If their FEV1 drops by >20% then they will be administered nebulised salbutamol as a bronchodilator.

Nasal sampling using nasosorption and nasal cytology brush may cause:

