- Nasal irritation and runny nose
- Minor epistaxis
- Watering of the eyes
- Sneezing

There are minimal if any side effects anticipated from the induced sputum procedure and salbutamol will be given as a bronchodilator at the same time of administration in healthy and asthma participants, but recognised side effects of the procedure include:

- Cough
- Tight chest

Expected AEs from blood sampling procedures may include:

- Mild discomfort during venepuncture
- Bruising at venepuncture site

11.4 *Suspected Unexpected Serious Adverse Reactions (SUSAR)*

A serious adverse reaction, the nature or severity of which is not consistent with the applicable product information

11.5 *Reporting Procedures for All Adverse Events*

All AEs occurring during the study observed by the investigator or reported by the participant, whether or not attributed to study, will be recorded on the CRF. The following information will be recorded: description, date of onset and end date, severity, assessment of relatedness to study and action taken. Follow-up information should be provided as necessary.

AEs considered related to the study as judged by a medically qualified investigator or the sponsor will be followed until resolution, or the event is considered stable. All related AEs that result in a participant's withdrawal from the study or are present at the end of the study, should be followed up until a satisfactory resolution occurs.

It will be left to the investigator's clinical judgment whether or not an AE is of sufficient severity to require the participant's removal from treatment. A participant may also voluntarily withdraw from treatment due to what he or she perceives as an intolerable AE. If either of these occurs, the participant must undergo an end of study assessment and be given appropriate care under medical supervision until symptoms cease or the condition becomes stable. The relationship of AEs to the study will be assessed by a medically qualified investigator.

11.6 *Reporting Procedures for Serious Adverse Events*

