All SAEs, except those expected ones defined in [section 10.3](#) that do not require immediate reporting, must be reported to the Sponsor within one working day of discovery or notification of the event. The Sponsor will perform an initial check of the information and ensure that it is reviewed at the next R&D Management meeting. All SAE information must be recorded on an SAE form and sent to the Sponsor using the appropriate reporting form and the contact details on there. Additional information

received for a case (follow-up or corrections to the original case) needs to be detailed on a new SAE form which must be sent to the Sponsor using the appropriate reporting form and the contact details on there.

The Sponsor will report all SUSARs to the Research Ethics Committee concerned. Fatal or life-threatening SUSARs must be reported within 7 days and all other SUSARs within 15 days. In addition to the expedited reporting above, the PI shall submit once a year throughout the study or on request an Annual Report to the Ethics Committee which lists all SAEs / SUSARs that have occurred during the preceding 12 months.

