15. CODES OF PRACTICE AND REGULATIONS

15.1 *Participant Confidentiality*

The study staff will ensure that the participants' anonymity is maintained. The participants will be identified only by initials and a participant's ID number on the CRF and electronic databases. All documents will be stored securely and only accessible by study staff and authorised personnel. The study will comply with the Data Protection Act 2018 which requires data to be anonymised as soon as it is practical to do so.

15.2 *Other Ethical Considerations*

The study will not be initiated before the protocol, and all study relevant material such as the PIS and ICF have received a favourable opinion from the Research Ethics Committee (REC) and the HRA, and Cambridge University Hospitals NHS Foundation Trust has issued trust confirmation of capacity and capability. Any changes to protocol or relevant study documents will be approved by the Sponsor. Should an amendment be made that requires REC approval, as defined by REC as a substantial amendment, the changes will not be instituted until the amendment has been reviewed and received favourable opinion from the REC and the HRA, and Cambridge University Hospitals NHS Foundation Trust have issued confirmation of continuing capacity and capability. A protocol amendment intended to eliminate an apparent immediate hazard to participants may be implemented immediately providing that the REC is notified as soon as possible, and an approval is requested. Minor amendments as defined by REC as a non-substantial amendment may be implemented upon receipt of HRA approval.

15.3 *Informed Consent*

It is the responsibility of the PI, or a person designated by the PI (if acceptable by local regulations), to obtain signed informed consent from each patient participating in this study, after adequate explanation of the aims, methods, anticipated benefits, and potential hazards of the study using the PIS.

The process for obtaining participant informed consent will be under the REC guidance, and GCP and any other regulatory requirements that might be introduced. The PI or delegate and the participant shall both sign and date the ICF before the person can participate in the study.

The participant will receive a written or electronic copy of the PIS and a signed and dated ICF. The ICF will also be printed and retained.

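### The tolerability condition in 10.2 governs only escalation; no visible rule spaces doses within a cohort or pauses the remaining volunteers at that level after a related SAE or rescue-level FEV1 fall

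*Combined protocol and SAP*

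**What the plan says.** Each volunteer receives one nebulised dose. Cohorts of six (four R848, two saline) step through 0.1, 1, 10 and 100 µg/mL in volunteers without asthma, and a cohort of six with asthma follows (7.1, 8.1, 10.2). The decision point in 10.2 is: "At the end of each dose cohort, CXCL10 levels in sputum and blood will be assessed and compared between saline and R848". If there is no significant difference "between groups, and the dose is tolerable for volunteers, then the study will proceed to the next dose cohort".

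The other safety provisions are these:

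- 10.2, on a symptomatic FEV1 fall of 20% or more: "Bronchodilator drugs will be available on standby for administration if volunteers have symptoms of breathlessness or tight chest".
- 11.3, for asthma: "If their FEV1 drops by >20% then they will be administered nebulised salbutamol as a bronchodilator".
- 9.6: "the investigator may discontinue a participant from the study at any time if the investigator considers it necessary for any reason".
- 11.5 leaves to the investigator's judgment "whether or not an AE is of sufficient severity to require the participant's removal from treatment".
- 11.6 has SAEs reported to the sponsor within one working day. The sponsor makes an initial check and must "ensure that it is reviewed at the next R&D Management meeting". SUSARs go to the ethics committee within 7 days (fatal or life-threatening) or 15 days (others).
- 15.2: "A protocol amendment intended to eliminate an apparent immediate hazard to participants may be implemented immediately".

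Appendix B schedules spirometry and observations at 15 minutes and 1, 4, 8 and 24 hours after challenge. No interval between volunteers and no daily dosing limit is stated.

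**The concern.** With a single dose per person, withdrawing someone who has reacted does not undo the exposure. What can still be limited is the exposure of volunteers not yet dosed. The escalation condition protects those at the next level, but no visible rule protects those still waiting at the same level. The asthma cohort comes last, so an escalation condition cannot protect anyone within it.

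The gap matters for two reasons. Finding a tolerable inhaled dose is the second aim in the synopsis. The human R848 experience cited in 10.1 is oral, dermal and nasal, with no prior inhaled R848 data, while the planned steps are tenfold and 5.2 itself stresses that the nose and lungs differ.

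**Working it through.** **Plan's own figure.** 6 sample-only + 4 × 6 without asthma + 6 with asthma = 36, as in the synopsis. If all four levels are used, and the asthma cohort is split 4:2 like the others, 5 × 4 = 20 volunteers receive R848.

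**Does any provision hold the next dose at the same level?**

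| Provision | Acts on | Holds the next same-level dose? |
|---|---|---|
| 10.2 tolerability condition | Next cohort | No |
| 10.2 FEV1 fall ≥20% with symptoms | The reacting volunteer (bronchodilator) | No |
| 11.3 FEV1 fall >20%, asthma | The reacting volunteer (salbutamol) | No |
| 9.6, 11.5 | One participant | No |
| 11.6 sponsor check, R&D meeting, SUSAR reports | Sponsor and ethics committee | No |
| 15.2 urgent amendment | The protocol | Possible, but no trigger is set |

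**Illustration of size.** The documents give no reaction rate and no dosing sequence. I assume a rate p per R848 recipient, independent reactions and dosing one at a time. With q = 1 − p and four R848 recipients:

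- P(at least one) = 1 − q⁴. At p = 5%: 1 − 0.8145 = 0.185. At p = 10%: 1 − 0.6561 = 0.344.
- P(two or more) = P(at least one) − 4pq³. At 5%: 0.1855 − 0.1715 = 0.014. At 10%: 0.3439 − 0.2916 = 0.052.
- P(a further reaction, given one) is the ratio of these: 7.6% at 5% and 15.2% at 10%.
- Mean R848 doses remaining after the first reaction = p(3 + 2q + q²) / P(at least one). At 5%: 0.2901 / 0.1855 = 1.56. At 10%: 0.561 / 0.3439 = 1.63. The maximum is 3.
- P(first reactor is the last R848 recipient) = pq³ / P(at least one): 23% at 5% and 21% at 10%. In those cohorts a pause spares no R848 dose.
- If every pause became permanent, expected reactors per cohort would fall from 4p to P(at least one): from 0.200 to 0.185 at 5%, and from 0.400 to 0.344 at 10%.

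**Dependence on spacing.** Over all 15 orderings of four R848 and two saline at p = 10%, the mean R848 doses remaining after the first reaction are 1.63 if dosed singly, 1.32 in pairs, 0.995 in threes and 0 if all six are dosed together. A pause rule therefore does little without spacing.

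**Which rates are plausible for SAEs.** The protocol reports no SAE in 54 nasal recipients. The one-sided 95% upper limit is 1 − 0.05^(1/54) = 5.4%, for another route with doses pooled. At 5.4%, two or more in a cohort has probability of about 1.6%.

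**Calendar.** Six volunteers dosed singly with a 24-hour review need five intervals, so at least 5 days. Thirty dosed volunteers over the stated 3 years average one per 3 × 365.25 / 30 = 36.5 days if spread evenly.

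**The case against.** The strongest reply is that the risk is already low and the team would stop anyway. The starting concentration is 100-fold below the nasal one. The top dose is about 100 µg (100 µg/mL × about 1 mL), against 700 µg oral reported as well tolerated. Asthma entry requires ACQ-5 ≤1.5 and FEV1 ≥70% predicted. Each volunteer is monitored for 24 hours by the team that doses the next one (9.4.1, 10.4), and at an even recruitment pace each 24-hour result would be known before the next dose. All of this stands, and it lowers the chance of harm. It does not state what happens to the next volunteer once a reaction occurs, and nothing guarantees even spacing.

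A reader might infer that the protocol requires the rest of the cohort to be dosed after a reaction. It does not. In 10.2 the end-of-cohort timing introduces the CXCL10 comparison; tolerability is a condition for proceeding, and nothing says it is considered only then. The text is silent, and silence is not an instruction. Nor is it right to infer that there is no oversight: the sponsor's initial check, the SUSAR reports and the investigator's discretion are real, though none is a dosing hold.

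The choice of FEV1 threshold is also open to debate. The protocol accepts a positive methacholine challenge, defined by PC20, as screening evidence in asthma, so pausing a cohort for one asymptomatic fall just over 20% is a judgment for the sponsor.

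**Conclusion.** The point holds as a gap in the visible text: the one dose-level safety condition concerns escalation, and no rule spaces or pauses dosing within a level or follows the asthma cohort. A rule in the Appendix A flowchart or in the SOPs mentioned in section 14 cannot be excluded.

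The size is modest. Up to three further R848 recipients could be dosed after a first reaction. At assumed rates of 5% to 10%, the chance of a further reaction in such a cohort is 8% to 15%. A reader might take the average of about 1.6 remaining doses as doses that a pause would save. It is an upper bound, because dosing may resume after review. A reader might also apply much higher reaction rates, such as 25% or 50%, but the documents give no basis for them. The figures further assume independent reactions and one-at-a-time dosing. The case for change is a cheap gain in volunteer safety; it does not rest on evidence that harm is likely.

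**What to change.** If a pause rule exists in the flowchart or an SOP, cite it in 10.2. Otherwise add to 10.2:

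- In every cohort, including asthma, the next volunteer is dosed only after the previous volunteer's spirometry and observations through 24 hours have been reviewed.
- Any related SAE pauses dosing at that level. So does a post-challenge FEV1 fall of at least 20% from baseline with breathlessness or chest tightness, occurring before the 24-hour sputum induction. The pause lasts until a documented investigator and sponsor review decides whether to resume. This is the protocol's own rescue trigger; the sponsor may set another, including a separate one for asthma. The cut-off keeps falls caused by sputum induction from counting. Later FEV1 falls would pause dosing only if they amount to a related SAE.

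In 11.6, let the one-working-day SAE report trigger this review, so that it does not wait for the next R&D Management meeting. With two joint sponsors (17.4), name who reviews.

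The cost is an amendment and at least 5 days from first to last dose in a cohort of six, using measurements already scheduled. Pauses would not be rare: about 19% to 34% of cohorts at rates of 5% to 10% in R848 recipients, plus any triggered by saline recipients, and some for unrelated events. If a level is stopped, its CXCL10 comparison may have fewer than four R848 recipients. Participant blinding is unaffected, since the PI or a delegate already prepares each solution (8.4).
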